# Merck Investigator Studies Program (MISP) Protocol Template

## Requirements for Submitting a Full Proposal

### Section #1 - MISP Protocol Identification

Study Title:	Comparative Assessment of Tedizolid Tissue Penetration and Pharmacokinetic Profile Between Diabetic Patients With Wound Infections and Healthy Volunteers via In Vivo Microdialysis
Request Date:	26-AUG-2015
Protocol Version Date:	11-JAN-2017
Institution Name	Center for Anti-Infective Research and Development Hartford Hospital
Investigator Contact Information: – Full address – Phone No. – Fax No. – e-mail address	[name], FCCP, FIDSA Center for Anti-Infective Research and Development Hartford Hospital [name] [contact] [contact] Email: [contact]

Section #2- Core Protocol	
2.1 Objectives & Hypotheses	
2.1.1 Primary Objectives: To describe the pharmacokinetic profile of oral tedizolid in the plasma and subcutaneous tissue of diabetic patients with ongoing wound infections of the lower extremities, i.e., below the knee, (study group) and compare it to the profile in healthy volunteers (control group) using in vivo microdialysis.
 
2.1.2 Secondary Objectives: To describe the safety and tolerability of oral tedizolid in diabetic patients with diabetic foot infections and in healthy volunteers

2.2 Background & Rationale, Significance of Selected Topic & Preliminary Data	
The annual incidence of foot ulcers among diabetics has been estimated at between 6% to 11.5%, and 10 to 15% of those with diabetes will have at least one foot ulcer during their lifetime. The majority (upwards of 60%) of these diabetic ulcers become infected. Treatment of these complicated diabetic wound infections primarily involve surgical intervention, topical antiseptics, and systemic antibiotic therapy. However, despite advances in these areas, outcomes from such infections remain poor and often lead to limb amputation in 15% to 20% of participants within 5 years.
 
Gram-positive organisms, particularly Staphylococcus aureus, are the main pathogens found in diabetic wound infections. As antibiotic resistance rates have risen, methicillin-resistant S. aureus (MRSA) has also become more frequent in acute bacterial skin and skin structure infections (ABSSSI). Additionally, diabetic wound infections caused by MRSA are associated with worse outcomes compared with other pathogens. As a result, antibiotics targeting MRSA are often prescribed for the treatment of diabetic wound infections either as monotherapy, or in combination with other antibiotics to cover Gram-negative and anaerobic bacteria that also may be present.
 
Tedizolid (Sivextro®, Cubist Pharmaceuticals Inc., Lexington, MA), the active moiety of the prodrug tedizolid phosphate, is an oxazolidinone antibiotic approved by the FDA for the treatment of ABSSSI caused by S. aureus (including MRSA), Streptococcus pyogenes, Streptococcus agalactiae, and Enterococcus faecalis. A 6-day course of tedizolid was well-tolerated and non-inferior to 10-day course of linezolid in Phase II and Phase III clinical trials of ABSSSI.
 
The pharmacokinetic profile of tedizolid has been described in numerous patient populations. However, the penetration into tissue during an active infection has yet to be elucidated. The most accurate method to calculate overall penetration is to evaluate the entire drug exposure, or AUC, in the tissue of interest and compare this with the overall AUC in blood. In the setting of clinical infection, our group has successfully applied a technique called in vivo microdialysis to assess the interstitial (i.e., extracellular) concentration profile of antimicrobials in comparison to their systemic exposures. This approach involves placing a probe with a semi-permeable membrane at the tip into tissue and constantly perfusing the probe with a physiologic solution via a pump; this approach allows for the continuous collection of extracellular fluid from the tissue and enables assessment of drug concentration over a specified time period (i.e., the entire dosing interval). Using this methodology, the penetration of a single 600 mg oral dose of tedizolid into muscle and subcutaneous adipose tissue of the thigh was assessed in 12 healthy volunteers. Tedizolid demonstrated an <math>AUC_{\text{tissue}}/AUC_{\text{plasma}}</math> ratio of 1.1 and 1.2 for adipose tissue and muscle, respectively, indicating excellent tissue penetration for the oral route of the drug administration into healthy volunteers. Although these data are promising, the


	
tissue penetration into actively infected tissue may vary from that of healthy volunteers. Furthermore, the dose tested was three-fold greater than the currently approved dosage of tedizolid. Because ABSSSI are very common in the diabetic patient and tedizolid may be a suitable oral therapeutic option, a study examining the tissue penetration of oral tedizolid in this population with ongoing infection is required to provide a more complete understanding of the pharmacokinetic profile of this novel compound. Hence a more comprehensive assessment of the interstitial fluid concentrations at the site of infection will serve as the pharmacologic basis for the clinical utility of tedizolid in the infected diabetic patient.
															

2.3 Study Design
	
2.3.1 Sites  The study will be conducted at Hartford Hospital, Hartford, CT. For participants enrolled in the study group (i.e., infected diabetic patients), all study interventions will occur while admitted as a Hartford Hospital inpatient. For participants enrolled in the control group (i.e., healthy adult volunteers), study interventions will occur in a study physician's office (baseline screening), at a local clinical laboratory (baseline laboratory screening), and in the Clinical Research Center (CRC) at Hartford Hospital.
 
2.3.2 Inclusion Criteria  2.3.2.1 Study Group  Participants with a documented medical history of Type 1 or Type 2 diabetes (for which they are receiving insulin or oral anti-hyperglycemic agents), and a suspected complicated skin and skin structure infection will be included. The suspected infection will be an ongoing and infection will be defined as mild or moderate by the Infectious Diseases Society of America, or as Grade 2 or 3 by the International Consensus on the Diabetic Foot (Table 1). Other anti-infective agents besides the study drug, except linezolid, will be permitted for the purposes of treatment.
 
Table 1. Clinical Classification of Infections
 
  
 Clinical manifestations of infection	Infection severitya	PEDIS gradeb	
   
 Wound lacking purulence or any manifestations of inflammation	Uninfected	1	
 
 Presence of <math>\geq 2</math> manifestations of inflammation (purulence, or erythema, pain, tenderness, warmth, or induration), but any cellulitis/erythema extends <math>\leq 2</math> cm around the ulcer, and infection is limited to the skin or superficial subcutaneous tissues; no other local complications or systemic illness	Mild	2	
 
 Infection (as above) in a participant who is systemically well and metabolically stable but which has <math>\geq 1</math> of the following characteristics: cellulitis extending <math>>2</math> cm, lymphangitic streaking, spread beneath the superficial fascia, deep-tissue abscess, gangrene, and involvement of muscle, tendon, joint or bone	Moderate	3	
 
 Infection in a participant with systemic toxicity or metabolic instability (e.g., fever, hypoglycemia, metabolic acidosis)	Severe	4	
  
	Clinical manifestations of infection	Infection severitya	PEDIS gradeb	Wound lacking purulence or any manifestations of inflammation	Uninfected	1	Presence of $\geq 2$ manifestations of inflammation (purulence, or erythema, pain, tenderness, warmth, or induration), but any cellulitis/erythema extends $\leq 2$ cm around the ulcer, and infection is limited to the skin or superficial subcutaneous tissues; no other local complications or systemic illness	Mild	2	Infection (as above) in a participant who is systemically well and metabolically stable but which has $\geq 1$ of the following characteristics: cellulitis extending $>2$ cm, lymphangitic streaking, spread beneath the superficial fascia, deep-tissue abscess, gangrene, and involvement of muscle, tendon, joint or bone	Moderate	3	Infection in a participant with systemic toxicity or metabolic instability (e.g., fever, hypoglycemia, metabolic acidosis)	Severe	4
Clinical manifestations of infection	Infection severitya	PEDIS gradeb														
Wound lacking purulence or any manifestations of inflammation	Uninfected	1														
Presence of $\geq 2$ manifestations of inflammation (purulence, or erythema, pain, tenderness, warmth, or induration), but any cellulitis/erythema extends $\leq 2$ cm around the ulcer, and infection is limited to the skin or superficial subcutaneous tissues; no other local complications or systemic illness	Mild	2														
Infection (as above) in a participant who is systemically well and metabolically stable but which has $\geq 1$ of the following characteristics: cellulitis extending $>2$ cm, lymphangitic streaking, spread beneath the superficial fascia, deep-tissue abscess, gangrene, and involvement of muscle, tendon, joint or bone	Moderate	3														
Infection in a participant with systemic toxicity or metabolic instability (e.g., fever, hypoglycemia, metabolic acidosis)	Severe	4														

chills, tachycardia, hypotension, confusion, vomiting, leukocytosis, acidosis, severe hyperglycemia, or azotemia)

a Infectious Diseases Society of America; b International Consensus on the Diabetic Foot; PEDIS, perfusion, extent/size, depth/tissue loss, infection, and sensation

#### ***2.3.2.2 Control Group***

Male or female healthy adult ( $\geq 18$  years of age) volunteers who will be identified via hospital and local advertisements (newspaper, postings, and internet) in the Greater Hartford, Connecticut region would be eligible to be enrolled.

#### ***2.3.3 Exclusion Criteria***

Participants in the study or control group will be excluded if any of the following criteria are met:

1. Less than 18 years of age
2. History of hypersensitivity to tedizolid or linezolid
3. History of hypersensitivity to lidocaine or lidocaine derivatives
4. Pregnant or breastfeeding
5. Presence of anemia, thrombocytopenia, or leukopenia as defined by hematocrit, platelet, or white blood cell count  $< 75\%$  of the lower limit of normal
6. Concomitant receipt of linezolid
7. Any other reason felt by the investigator to potentially affect the outcomes of the study

##### ***2.3.3.1 Additional Exclusion Criteria for Study Group***

1. Participants likely to require multiple surgical interventions during the study period, which therefore could affect placement of the microdialysis catheter

##### ***2.3.3.2 Additional Criteria for Control Group***

1. Positive urine drug screen (cocaine, THC, opiates, benzodiazepines, and amphetamines).
2. History of regular alcohol consumption exceeding 7 drinks/week for females or 14 drinks/week for men (1 drink = 5 ounces of wine or 12 ounces of beer or 1.5 ounces of hard liquor) within 6 months of screening.
3. Use of tobacco- or nicotine-containing products in excess of the equivalence of 5 cigarettes per day.
4. Use of prescription or nonprescription drugs, vitamins, or dietary supplements within 7 days or 5 half-lives (whichever is longer) prior to the first dose of study medication, with the exception of acetaminophen at doses of  $\leq 1$  g/day. Herbal supplements, hormonal methods of contraception (including oral and transdermal contraceptives, injectable progesterone, progestin subdermal implants, progesterone-releasing IUDs, postcoital contraceptive methods), and hormone replacement therapy must be discontinued at least 14 days prior to the first dose of study medication. Depo-Provera® must be discontinued at least 6 months prior to the first dose of study medication.

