2.5 Study Procedures	
2.5.1 Screening Procedure
 
2.5.1.1 Study Group
 
Electronic medical records of admitted diabetic patients who are being followed by podiatrists for infections of the lower limbs will be pre-screened to identify patients eligible for study enrollment through evaluating each patient's profile for the meeting of inclusion and exclusion criteria. Pre-screening will involve accessing patient's medical record to determine eligibility. If eligible, written informed consent will be obtained (see 2.5.2) followed by complete screening, which will include a physical exam, medical, surgical, and medication history and collection of blood and urine for laboratory assessment (see 2.5.5.1). Screening will occur within 24 hours of the first dose of tedizolid.
 
2.5.1.2 Control Group
 
Adult healthy volunteers will be identified via hospital and local advertisements (newspaper, postings, and internet) and will be initially pre-screened via phone interview. If eligible, all volunteers will be screened by a study physician within 28 days of the scheduled study period to confirm that inclusion and exclusion criteria are met after providing written informed consent (see 2.5.2). This will include a physical exam, medical, surgical, and medication history and collection of blood and urine for laboratory assessment (see 2.5.5.1).
 
2.5.2 Informed Consent
 
Prior to study enrollment, patients and healthy volunteers identified as eligible for the study will be approached for consenting, where they will be provided with written informed consent that will document their election and agreement to participate in the study. The consenting process will be conducted by the principal investigator, co-investigators, or trained research staff members. A copy of the signed consent will be provided to the participant and placed in the medical record (study group only).

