### **2.5.3 Study Drug**

All participants will receive tedizolid phosphate 200 mg orally every 24 hours. The study group will receive 3-6 doses, to allow flexibility in sample collection among other medical/surgical interventions required during his/her hospitalization. The control group will receive 3 doses to achieve steady-state before sample collection. All participants in the study group will also receive standard intravenous or oral antibiotic therapy to treat their diabetic foot infections.

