### **2.5.5 Procedures**

#### **2.5.5.1 Baseline Participant Evaluations**

At screening, eligibility will be verified using inclusion/exclusion criteria. A general physical examination, including pedal pulses (study group only), a medical/surgical/medication history and vital signs (temperature, blood pressure, heart rate, respiratory rate) will be conducted by the study physician. Clinical laboratory tests, including serum electrolyte panel, serum creatinine, liver function panel, complete blood count with differential, glycosylated hemoglobin (HbA1c)(study group only), albumin, and microscopic urinalysis will be performed unless drawn within the last three days and the participant is clinically stable. Urine pregnancy tests will be required for women of childbearing potential. Concomitant medications will be recorded. A blood sample for screening of common drugs of abuse (cocaine, tetrahydrocannabinol (THC), opiates, benzodiazepines, and amphetamines) will be collected (control group only).

Study group participants will be screened within 24 hours of first dose of tedizolid. Control group participants will be screened within 28 days of first dose of tedizolid.

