#### **2.5.5.2 Clinical Research Center (CRC) – (Control group only)**

Once enrolled and confirmed eligible at baseline screening, control group participants will be admitted to the CRC at Hartford Hospital on the evening of Study Day -1. A second screening of selected control group participants, which will include a brief physical exam, vital signs, medical history, and repeat of all labs tested in 2.5.5.1 except for drugs of abuse screening, will take place. This is to confirm study eligibility is maintained. Study drug will be administered on Study Days 1, 2, and 3. A microdialysis catheter (see 2.5.5.3) will be inserted on Study Day 3, followed by blood and dialysate collection (see 2.5.5.5 and 2.5.5.6). A final end of study physical exam and collection of blood and urine for laboratory assessment will be conducted on Study Day 4 before discharge. On Study Days 1 and 2 (only), participants are permitted to leave the CRC for work/school or at discretion of the Principal Investigator after oral dosing and a 4 hour monitoring period. Participants must return to the CRC for dinner time (7pm) on the same day. During the remainder of the study (Day 3 and Day 4), participants will not be permitted to leave the CRC. Lunch and Dinner will be provided for participants while they are in the CRC. Participants must refrain from consuming caffeinated and alcoholic beverages during the study (Day -1 to Day 4)..

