	
2.5.5.7 Protein Binding Analysis and Determination
 
Protein binding studies will be conducted using Centrifree® Ultrafiltration devices (Millipore Corporation, Billerica, MA).. An additional blood sample of 20 mL will be collected at the estimated peak concentration (3 hours after the dose was administered) into two 10-mL BD Vacutainer® tubes containing sodium heparin (green top). Samples will be immediately centrifuged to collect the separated plasma. Approximately 0.9 mL of plasma will be transferred into six separate ultrafiltration devices, three devices per filter type, and centrifuged for 45 minutes at 25 °C at 2,000 × g to generate an ultrafiltrate volume of approximately 250 µL. In addition, an aliquot of plasma will be retained for total drug concentration determinations and will be kept frozen at -80°C.
 
In addition, non-specific binding to the ultrafiltration membrane will be determined at a single tedizolid concentration similar to the peak observed in patients. For these studies, an aqueous standard of tedizolid will be prepared in accordance to manufacturer's recommendation and ultrafiltration will be performed as outlined above for both ultrafiltration devices..
 
Individual protein binding percentages will be applied to each participant's data at each time point to determine free plasma concentrations. The percentage of protein binding will be calculated using the following formula: % Protein Binding = 100 – (Concentrationultrafiltrate / Concentrationplasma × 100).
 
2.5.5.8 Study Exit Evaluation
 
After completion of all sampling and removal of microdialysis catheters, an end of study exit evaluation will occur. This will include a full physical examination, including vital signs. Blood and urine will be collected to repeat all labs tested in 2.5.5.1, except for the pregnancy test and drugs of abuse screening. All abnormal determinations will be followed until resolution unless follow-up is determined to be unnecessary by the study physician. For the control group, participants will be discharged from the study after a 4 hour monitoring period from removal of microdialysis catheters.
 
2.5.5.9 Determination of Tedizolid Concentrations
 
Tedizolid concentrations in plasma, dialysate fluid, and aqueous standards will be assessed using validated high performance liquid chromatography (HPLC) assays at the Center for Anti-Infective Research and Development of Hartford Hospital.

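### Healthy women must stop hormonal contraception at least 14 days before dosing, but no eligibility criterion requires abstinence or a non-hormonal method instead

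*Combined protocol and SAP*

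**What the plan says.** The control group is open to healthy adults of either sex (section 2.3.2.2), and six are planned (section 2.7.4). Control criterion 4 in section 2.3.3.2 covers recent medication. Among the products to be stopped it names "hormonal methods of contraception (including oral and transdermal contraceptives", then injectables, implants, progesterone-releasing IUDs and postcoital methods. It ends by saying that these and "hormone replacement therapy must be discontinued at least 14 days prior to the first dose of study medication". Depo-Provera has its own limit of at least 6 months.

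The pregnancy safeguards are as follows:

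- Section 2.3.3, item 4, excludes anyone "Pregnant or breastfeeding".
- Section 2.5.1.2 sets the screening window: "all volunteers will be screened by a study physician within 28 days of the scheduled study period".
- Section 2.5.5.1, on screening: "Urine pregnancy tests will be required for women of childbearing potential".
- The section on the Clinical Research Center (2.5.5.2) provides on Day -1 for a "repeat of all labs tested in 2.5.5.1 except for drugs of abuse screening".
- Section 2.5.5.8, on the exit visit, says to "repeat all labs tested in 2.5.5.1, except for the pregnancy test and drugs of abuse screening".

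On dosing, section 2.5.3 states: "The control group will receive 3 doses to achieve steady-state before sample collection". Each dose is 200 mg, given on Study Days 1, 2 and 3.

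**The concern.** A volunteer who relies on hormonal contraception has to give it up to enter the study, and no eligibility criterion asks her to put anything in its place. Non-hormonal methods and abstinence remain open to her, but neither is required. The pregnancy test detects an established pregnancy. It does not prevent one, and it cannot see a very recent conception.

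A woman could therefore follow criterion 4 to the letter, meet every listed criterion, test negative on Day -1 and take three doses in early pregnancy. Exclusion 4 exists to prevent that. Nothing later in the schedule would reveal it, because the test is dropped at exit. She is a healthy volunteer with no infection to treat, so she has no therapeutic benefit to set against the exposure.

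Only participant safety is at stake. The penetration ratio, the plasma parameters and the group comparison are unaffected.

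**Working it through.** **Is a replacement method required anywhere?** The places where it could stand are the inclusion criteria (2.3.2), the general and group-specific exclusions (2.3.3 to 2.3.3.2), screening and consent procedures (2.5.1, 2.5.2), baseline evaluations (2.5.5.1), the Clinical Research Center stay (2.5.5.2) and the exit evaluation (2.5.5.8). None mentions abstinence, a barrier or other non-hormonal method, or sterilisation. General exclusion 7 gives the investigator discretion, but over matters that could affect the study outcomes; it is not a contraception rule.

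**Is the pregnancy test repeated on Day -1?** Yes, by cross-reference. The Day -1 repeat omits only the drug screen. The exit visit uses the same cross-reference and has to remove the pregnancy test by name, which shows that the test counts among those labs unless excepted. Screening may fall anywhere in the 28 days before dosing, so it may come before the woman stops her contraception. Day -1 is the only test certain to follow the stop, and it is also the last.

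**How long is she without the method?** At least 14 days before Day 1, plus the 3 days from Day 1 to Day 4: 14 + 3 = 17 days. The stay does not confine her throughout, since volunteers may leave after dosing and a 4-hour monitoring period on Days 1 and 2.

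**What can the Day -1 test miss?** The plan gives no figure to reproduce. Inputs:

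- Stop at the 14-day minimum: t = 0.
- First dose, Day 1: t = 14.
- Day -1 test: t = 13, taking Day -1 as the day before Day 1.
- L = days from conception to a positive urine test. The documents do not give this; I assume 10 to 16.

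The test misses conceptions at t > 13 − L, so it misses min(L, 13) of the 13 days between stop and test. Counted back from the first dose, the undetected window begins L + 1 days earlier.

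| Assumed lag L | Days missed, of 13 | Window opens, days before dose 1 |
|---|---|---|
| 10 | 10 | 10 + 1 = 11 |
| 13 | 13 | 13 + 1 = 14 |
| 16 | 13 (capped) | 16 + 1 = 17 |

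The screening test is never later than Day -1, so it finds no conception that the Day -1 test would miss.

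**How much would a contraception requirement starting at least 14 days before dose 1 cover?** Uncovered days = max(0, L + 1 − 14):

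- L = 10: max(0, −3) = 0.
- L = 13: max(0, 0) = 0.
- L = 16: max(0, 3) = 3.

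The 3 days matter only for a woman who stopped earlier than the minimum, or never used hormones, and who consents less than 17 days before dose 1. If the requirement starts 17 or more days before dose 1, the residual is 0.

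**The case against.** The best case for leaving the text alone has five parts.

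1. **Harm is not shown.** No passage supplied states a fetal risk for tedizolid. The exposure is three doses in six volunteers, and there may be no woman on hormonal contraception among them. This is correct. It limits the size of the point, which rests on the protocol's own exclusion of pregnancy rather than on a documented hazard.

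2. **The exclusion is already enforced.** There are two tests, the last on the evening before dosing, and the remaining blind period applies to any woman of childbearing potential. That is also true. What criterion 4 adds is the required withdrawal of a method already in use, and the tests do not make up for it.

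3. **The consent pages were removed and may give contraception advice.** They may, and nothing here says that volunteers go unadvised. But advice in a consent form is not an eligibility criterion that staff verify at screening and again on Day -1. The point is confined to the criteria.

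4. **The scenario is narrow.** A woman may decline to take part, and the 6-month Depo-Provera limit, far longer than the 28-day screening window, must act mostly as a history check. The scenario also needs a stop at the minimum, no substitute and a conception within about two weeks, and the day counts depend on an assumed lag. All of this stands as a reason for modesty. The 14-day rule can still impose a withdrawal.

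5. **The remedy does not match the complaint.** It would bind control women who never used hormones and would do nothing for study-group women, who may take 3 to 6 doses. Both are true. The wider reach is harmless, since those women share the test's blind period. Criterion 4 does not apply to the study group, so no method is withdrawn there.

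**Conclusion.** The concern holds. Control criterion 4 makes giving up hormonal contraception a condition of entry, and no eligibility criterion supplied requires anything in its place. For a woman who stops at the 14-day minimum, the last pregnancy test cannot exclude conception on 10 to 13 of the 13 days before it.

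That range rests on the assumed lag of 10 to 16 days, on reading Day -1 as the day before Day 1, and on treating every day after the stop as one on which conception could occur. It does not measure the probability of pregnancy or of exposure, which cannot be derived from the documents and may be zero in this group. Confidence is medium, mainly because the consent pages are not available. The change should be made because the protocol itself creates the gap and closing it costs very little, not because a large risk has been shown.

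**What to change.** Add one criterion to section 2.3.3.2:

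> Women of childbearing potential must use abstinence or an effective non-hormonal method of contraception from consent, or from 14 days before the first dose if that is earlier, through study exit.

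Leave the washout and the pregnancy-test schedule as they are. If consent comes less than 14 days before the first dose, check the days before consent by history at screening.

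The cost is one sentence, with no added visit, sample or procedure. A few more volunteers may fail screening while six places are filled; the documents do not allow that number to be estimated. If the consent form already gives this advice, the sentence simply brings the criteria into line with it.
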